4.5. Subgroups

Analyses of per-subject recall rate for non-cancer cases and specificity are limited to the subgroup of cases without cancer. Analyses of per-subject sensitivity and per-subject recall rate for cancer cases are limited to the subgroup of subjects with cancer. We may also 1) analyze recall rate in the subgroups of non-cancer recall, normal, and benign cases; 2) perform per-lesion analysis of sensitivity in subgroups defined by lesion type (masses with or without calcifications, focal asymmetries, and/or architectural distortions in one subgroup, and calcifications in another subgroup); and/or 3) analyze AUC, sensitivity, specificity, and/or recall rate in the subgroups of women with dense or non-dense breasts.

4.6. Analysis of Study Endpoints

4.6.1. Primary Endpoint

The primary endpoint on this study is non-inferior per-subject average AUC requiring correct lesion localization. Primary analysis will not involve pooling across study radiologists, to allow for heterogeneity across them. We will estimate AUCs for each reader in each review condition (FFDM, DBT plus S-View) based on per-subject POM scores requiring correct lesion localization derived as in **Section 4.4**, above. The non-inferiority margin for this endpoint is delta = 0.05.

We will provide graphs of each reader's ROC curve for each review condition. For each reader, the non-parametric (trapezoidal) AUC for the FFDM read, the DBT plus S-View read, and the difference between them, will be presented. Statistical inferences will account for correlations arising from having all study readers interpret all study cases. We plan to compare AUCs between reading conditions using the standard MRMC analysis of variance (ANOVA) method of Obuchowski and Rockette⁶ adjusted for estimation in the F* test statistic⁷, to ensure generalization of the study results to both the population of readers and the population of cases. Two-sided 95% CIs will be used to quantify uncertainty in the within-modality estimates and the between-modalities differences.

Modeling framework. Let A_{ij} be an estimate of the AUC in modality *i* (*i* = 1 for FFDM, 2 for DBT plus S-View) for the *j*th radiologist (*j* = reader 1, ..., *R* for *R* = 18). We consider the effects of radiologists to be random, because interest extends beyond the radiologists on this study to a larger population of potential radiologists from which these radiologists are a sample. Obuchowski and Rockette⁶ model these estimates using mixed effects ANOVA, as

$$A_{ij} = \mu + \alpha_i + b_j + (\alpha b)_{ij} + e_{ij}$$

where

- μ is the overall AUC across the populations of readers and cases,
- α_i is the fixed effect of modality,
- b_j is a random effect for reader with expectation 0 and variance σ_b^2 with random effects for different readers independent of each other,

- $(\alpha b)_{ij}$ is a random effect for the interaction of modality and reader with expectation 0 and variance σ^2_{ab} also with random effects for different readers independent of each other, and
- e_{ij} is random error with expectation 0, variance $\sigma_c^2 + \sigma_w^2$ for σ_c^2 the case sample variance and σ_w^2 the within-reader variance, and covariance
 - $r_1 \sigma_c^2$ for two AUCs from the same reader in different modalities,
 - $r_2 \sigma_c^2$ for two AUCs from different readers in the same modality, and
 - $r_3 \sigma_c^2$ for two AUCs from different readers in different modalities.
- The random effects b_j , $(\alpha b)_{ij}$, and e_{ij} are independent of each other.
- When the readers review the case sample only once in each modality $(\alpha b)_{ij}$ and e_{ij} are not identifiable, and we cannot separate σ^2_{ab} from $\sigma^2_c + \sigma^2_w$.

We will obtain the average AUC within each modality and its standard error, and the average difference in AUC for DBT plus S-View – FFDM and its standard error. We will use these to compute corresponding two-sided 95% CIs for the average AUC within each modality and for their difference, all referencing a Student's *t*-distribution with degrees of freedom adjusted for estimation in Obuchowski and Rockette's⁶ adjusted F-statistic.⁷

The study will be considered to have successfully demonstrated safety and effectiveness of the Fujifilm ASPIRE Cristalle DBT plus S-View system if the per-subject average AUC for DBT plus S-View is statistically significantly non-inferior to the average AUC for FFDM at the alpha = 0.05 significance level, for non-inferiority margin delta = 0.05. This will be established if the lower limit of the two-sided 95% CI for the difference in average AUC for DBT plus S-View minus FFDM lies entirely above the negative of the non-inferiority margin, -0.05.

4.6.2. Secondary Endpoints

When analyzing secondary endpoints per-subject POM, BI-RADS, and recall scores requiring correct lesion localization will be derived as described in **Section 4.4**. Analyses of secondary endpoints also will use standard MRMC ANOVA methods^{6, 7} to compare performance metrics for DBT plus S-View versus FFDM, and two-sided 95% CIs to quantify uncertainty.

The secondary endpoints are:

- Non-inferior and/or superior (lower) per-subject average recall rate for all non-cancer cases, based on recall scores, using non-inferiority margin delta = 0.05.
- Non-inferior per-subject average recall rate for all cancer cases, based on recall score, using non-inferiority margin delta = 0.10.
- 3. Non-inferior and/or superior per-subject average sensitivity, based on BI-RADS scores requiring correct lesion localization, using non-inferiority margin delta = 0.10.
- Superior per-subject average AUC, based on POM scores and requiring correct lesion localization.
- 5. Non-inferior per-subject average specificity, based on BI-RADS scores.
- 6. Superior (lower) per-subject average recall rate for all follow-up proven non-cancer recall cases.
- Non-inferior per-lesion average sensitivity for masses, masses with calcifications, focal asymmetries, and/or architectural distortions, based on BI-RADS scores requiring correct lesion localization, using non-inferiority margin delta = 0.10
- Non-inferior and/or superior per-lesion average sensitivity for calcifications, based on BI-RADS scores requiring correct lesion localization, using non-inferiority margin delta = 0.10
- 9. Non-inferior (margin delta = 0.05 for AUC, 0.10 for other performance metrics) and/or superior average AUC and/or other performance metric(s) for subjects with dense breasts (BI-RADS breast composition categories c. The breasts are heterogeneously dense, which may obscure small masses and d. The breasts are extremely dense, which lowers the sensitivity of mammography).

Estimates and corresponding 95% confidence intervals illustrating precision in the estimates will be provided for, at a minimum: 1) per-subject average recall rate for all non-cancer cases and 2) for all cancer cases, 3) per-subject average sensitivity, and 4) per-subject average specificity. Analysis of each of these will be performed using standard MRMC ANOVA methods.^{6,7} Sensitivity, specificity, and recall rate each provide additional information needed to understand the expected impact of using DBT plus S-View on clinical practice. Their analysis

and reporting, including confidence intervals, is thus required to provide a complete description of device performance.

Analysis evaluating 5) superiority of per-subject average AUC will be performed similarly to analysis of the Primary Aim. Superiority will be established if the lower limit of the two-sided 95% CI for the difference in average AUC for DBT plus S-View – FFDM lies entirely above zero (0).

Analysis of 6) per-subject recall rate for all recall cases will be performed similarly to analysis of per-subject recall rates for all non-cancer cases. If analysis is performed in the subgroup of recall cases, complementary analysis will be performed in the subgroup of normal cases and in the subgroup of benign cases.

We plan to use methods for clustered data from MRMC studies that take into account the correlation between lesions in the same case when analyzing lesion-level sensitivity in 7) the subgroup of soft tissue lesions (masses, masses with calcifications, focal asymmetries, and/or architectural distortions) and 8) the subgroup of calcifications. In particular, Rao and Scott's⁸ method for estimating proportions from clustered data will be used to obtain estimates for each reader in each reading condition, and Obuchowski's⁹ extension of this to a pair of correlated proportions will be used to estimate the variance-covariance matrix of all possible pairs of proportions. The usual Obuchowski and Rockette^{6,7} MRMC method will then be applied to perform inferences that generalize to the population of readers and the population of cases while also taking into account within-case correlations between lesions. Analysis will be performed in either both subgroups, or in neither subgroup.

Analysis 9) in the subgroup of subjects with dense breasts will be performed similarly to corresponding analysis above. If analysis is performed in the subgroup of women with dense breasts, complementary analysis will be performed in the subgroup of women with non-dense breasts.

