Estimates and corresponding 95% confidence intervals illustrating precision in the estimates will be provided for, at a minimum: per-subject average recall rate for all non-cancer cases and for all cancer cases, per-subject average sensitivity, and per-subject average specificity. (Note: This information is provided for AUC as part of evaluation of the study's primary endpoint.). Sensitivity, specificity, and recall rate each provide additional information needed to understand the expected impact of using DBT plus S-View on clinical practice. Their analysis and reporting, including confidence intervals, is thus required to provide a complete description of device performance.

Multiple comparisons. To protect the study's Type 1 error rate from inflation we will use the iterative graphical approach described in Bretz, et al.¹ to sequentially reject hypotheses.

2. Study Design

Protocol FMSU2017-002B is a retrospective, MRMC study of Fujifilm DBT plus S-View to be conducted with an enriched sample of 300 cases obtained from multiple image acquisition centers on Fujifilm protocol FMSU2013-004A "Acquisition of Digital Mammography and Breast Tomosynthesis Images for Clinical Evaluation of Fujifilm Digital Breast Tomosynthesis," and approximately 18 radiologist readers with varying experience levels some of whom have limited experience reading 2D synthetic images. The study employs a fully factorial, counterbalanced crossover design in which all readers review images from all cases in two (2) visits separated by a memory washout period of approximately four (4) weeks. Each reader will read half the cases as FFDM and the other half as DBT plus S-View during Visit 1, and the complementary FFDM and DBT plus S-View images during Visit 2.

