4.6.3. Multiple Comparisons

We will use a graphical approach to illustrate relationships among endpoints and protect the study's type 1 error rate from inflation.^{1,10} The testing strategy is shown in a figure with vertices (nodes) for each hypothesis to be tested and directed paths (arrows) between vertices. All study hypotheses to be formally tested as potential marketing claims are shown in the graph.

Hypotheses are denoted H₁, H₂, ..., H_k, ..., H_m, where *m* is the total number of hypotheses to be tested. Each hypothesis to be tested is allocated initial endpoint specific alpha, α_k , and the sum $\alpha_1 + \alpha_2 + ... + \alpha_k + ... + \alpha_m = \alpha$ for the study overall, 0.05. Initial endpoint-specific alpha can be 0 for endpoints of lesser importance; hypotheses for these endpoints will receive alpha from hypotheses that are rejected and direct alpha toward them. Each directed path is assigned a weight between 0 and 1 indicating how much of the endpoint-specific alpha moves along the path when a hypothesis is rejected. The sum of weights leaving any hypothesis equal to 1, that is, all of the preserved alpha is used in receiving hypotheses. Paths may include a loop-back feature whereby if only one of a pair of looping hypotheses is rejected at its endpoint-specific α_k , that α_k loops back to the other hypothesis to increase its endpoint-specific alpha. Testing in a strategy with loop-back can start with any vertex that has initial endpoint-specific $\alpha_k > 0$, and all such vertices can be tested until one is found for which the null hypothesis is rejected; then testing follows the arrows. Finally, conditional passing of alpha is shown by paths with negligible weights epsilon (ε); this places higher priority on other hypotheses until those have been tested.

The graph is continually updated each time a null hypothesis is successfully rejected, as follows:

- 1. Pass α_k from successful H_k according to the path weights.
- 2. Eliminate the vertex for H_k .
- 3. Connect all incoming arrows to outgoing arrow tails of the deleted vertex.
- 4. Adjust path weights based on relative weights of previous parts of path. Maintain:
 - a) Sum of endpoint-specific $\alpha_k = \alpha$, and
 - b) Sum of outgoing weights from each vertex = 1.
- 5. If a new path duplicates an existing path, combine them and add their weights.

The hypotheses that Fujifilm is interested in testing on this study are shown in **Table 3** on the following page.

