Hypothesis	Endpoint	Null Hypothesis	Alternative Hypothesis	Non-inferiority margin, delta
H ₁	AUC	Inferior	Non-inferior	0.05
H ₂	Per-subject recall rate for all non-cancer cases	Inferior	Non-inferior	0.05
H ₃	Per-subject recall rate for all cancer cases	Inferior	Non-inferior	0.10
H ₄	Per-subject sensitivity	Inferior	Non-inferior	0.10
H ₅	Per-subject recall rate for all non-cancer cases	Equal	Superior	N/A
H ₆	Per-subject specificity	Inferior	Non-inferior	0.05
H ₇	AUC	Equal	Superior	N/A
H ₈	Per-subject sensitivity	Equal	Superior	N/A
N/A = Not applicable.				

 Table 3. Hypotheses That May Be Tested

General considerations for employing the graphical approach to protect the study's type 1 error rate from inflation, as presented in protocol section 12.6, are:

- H_1 corresponds to the study's primary endpoint. Testing will use the full study alpha: $\alpha_1 = \alpha = 0.05$. Hypothesis testing for secondary endpoints will only proceed if H_1 is rejected, in which situation α_1 will be passed to one or more of H_2 , H_3 , and/or H_4 through path weights w_{12} , w_{13} , and w_{14} , respectively. These weights will sum to 1, and one or two of them may be 0.
- H₂, H₃, and H₄ correspond to higher priority secondary endpoints. Their initial endpointspecific alphas are zero, because they are only tested if the study's primary aim is met. If that occurs their endpoint-specific alphas are updated to $\alpha_k = w_{1k} \times \alpha_1$. Each of H₂, H₃, and H₄ may pass alpha to either of the others, and this may involve loop-back. One or more of H₂, H₃, and/or H₄ also may pass alpha to one or more of H₅ through H₈, and this may be conditional on first testing all of H₂, H₃, and H₄.
- H₅ through H₈ correspond to secondary endpoints with lower priority and/or likelihood of success. Their initial endpoint-specific alphas are zero. Each of these may receive alpha

[figure not shown]
from H_2 , H_3 , and/or H_4 . Each of H_5 through H_8 may pass alpha to the others, and this may involve loop-back.

• Paths with weight 0 will not appear in the final graphic.

By approving this SAP, Fujifilm and the study's Principal Investigator confirm that this pre-specified statistical analysis plan (SAP) provides final path weights determined through discussion between Fujifilm, the study's Principal Investigator, and BCL. Path weights have been finalized prior to receiving any study reading data, as follows:

- H₁ passes alpha equally to each of H₂ and H₄.

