- H₂ and H₄ pass alpha to each other with path weights 1 − ε (epsilon) and to each of H₃ and H₅ with path weights ε/2.
 - The pair of infinitesimal path weights $\epsilon/2$ ensure that both H₂ and H₄ are tested before testing H₃ and H₅.
 - The loop-back provision between H_2 and H_4 ensures that if either the p-value for testing H_2 : inferior non-cancer recall rate or the p-value for testing H_2 : inferior sensitivity is less than alpha/2 (0.025), the other endpoint can be tested at alpha = 0.05 without inflating the study's type 1 error.
- H₃ and H₅ pass alpha to each other with path weights 1 − ε (epsilon), and to H₆ with path weight ε.
- H_6 passes its entire alpha to H_7 (path weight 1), and
- H_7 passes its entire alpha to H_8 (path weight 1).

The graphical approach with path weights is provided in Figure 1 on the following page.

Inf. = Inferior. AUC = Area under the receiver operating characteristic (ROC) curve. NonCan = Non-Cancer. Sens = Sensitivity. Can = Cancer. Eq. = Equal. Spec = Specificity.

Figure 1. Graphical Approach to Protect the Study's Type 1 Error Rate from Inflation

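### Does the dense-breast secondary endpoint (endpoint 9) open an uncontrolled route to a superiority claim?

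*SAP*

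**What the plan says.** SAP 1.1.2 and 4.6.2 list nine secondary endpoints. The ninth concerns women with dense breasts: non-inferior ("margin delta = 0.05 for AUC, 0.10 for other performance metrics) and/or superior average AUC and/or other performance metric(s"). Its method is one sentence in 4.6.2: "Analysis 9) in the subgroup of subjects with dense breasts will be performed similarly to corresponding analysis above". For AUC in the full case set, the same section says "Superiority will be established if the lower limit of the two-sided 95% CI for the difference in average AUC for DBT plus S-View" minus FFDM is above zero. SAP 1.1.2 follows its endpoint list with the statement "To protect the study's Type 1 error rate from inflation we will use the iterative graphical approach".

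SAP 4.6.3 sets out that approach. It says "All study hypotheses to be formally tested as potential marketing claims are shown in the graph". Its Table 3, titled "Hypotheses That May Be Tested", contains H1 to H8, all in the full case set. In the last listed path, H7 "passes its entire alpha to H_8 (path weight 1"). SAP 4.5 makes the dense-breast work optional; under a permissive lead-in it reads "3) analyze AUC, sensitivity, specificity, and/or recall rate in the subgroups of women with dense or non-dense breasts". SAP section 5 likewise makes the subgroup outputs conditional on the analyses being done.

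**The concern.** Four of the nine secondary endpoints (6 to 9) have no hypothesis in the graph, and no sentence calls them descriptive. Endpoint 9 stands out because it carries margins, superiority wording and an open choice of metric. Its method sentence points back to a section in which a 95% CI above zero establishes AUC superiority.

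In the full case set, AUC superiority is H7, reached in effect only after H1 to H6 are all rejected. If the same CI rule applied in dense breasts without that sequence, a subgroup claim could stand where the full-set claim could not be tested. The metric, and whether to analyse at all, could also be settled after results are seen. At stake would be the type 1 error protection promised in SAP 1.1.2.

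**Working it through.** **1. Where the alpha goes.** Initial alpha is 0.05 on H1 and 0 on H2 to H8, so the sum is 0.05. H1 splits its alpha equally between H2 and H4. Those two feed each other and, through infinitesimal weights, H3 and H5. H3 and H5 feed each other and then H6, which feeds H7, which feeds H8. Outgoing weights sum to 1 for each of H1 to H7, and none is listed for H8. No path leads to a dense-breast test, so endpoint 9 has alpha 0 and cannot take alpha from H1 to H8.

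**2. What the text says about status.**

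| Place | Effect on endpoint 9 |
|---|---|
| SAP 4.6.3, scope sentence | Hypotheses tested for claims are in the graph; endpoint 9 is not |
| SAP 4.6.3, H1 rule | No secondary endpoint is tested unless H1 is rejected |
| SAP 4.6.2 | CIs are mandatory only for recall (non-cancer and cancer cases), sensitivity and specificity in the full set; a dense-breast analysis requires a non-dense one |
| SAP section 5, full-set blocks | AUC results are used to judge non-inferiority and superiority; the block for the other metrics reports the graph's test results |
| SAP section 5, subgroup block | Reader tables, averages, 95% CIs and AUC plots; no line for test results |

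The section 5 contrast matters most: testing output is requested for the full set and left out where dense breasts are named.

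**3. Error if the plan were not followed.** Suppose a dense-breast CI above zero were presented as an established claim, with all true differences zero. Each metric then has a one-sided error of 0.025. For k independent metrics the chance of at least one false claim is 1 − 0.975^k:

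- k = 1: 0.025
- k = 4: 0.096
- k = 5 (AUC, sensitivity, specificity, recall in cancer and in non-cancer cases): 0.119, with a Bonferroni limit of 5 × 0.025 = 0.125

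The metrics are correlated, so these values are rough. They describe a departure from 4.6.3.

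**4. Does the H1 gate limit that error?** Hardly. With H1 power 92% and a correlation of 0.63 to 0.90 between the dense and full-set AUC differences (assumed), more than 99.9% of false dense-breast AUC results also pass H1. The protection comes from the scope sentence.

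**5. Precision in dense breasts.** SAP 4.10 gives var = (2/R){σ_ab² + σ_w² + σ_c²[1 − r1 + (R − 1)(r2 − r3)]}, with R = 18, σ_ab² = 0.0016 × 0.27 = 0.000432, σ_w² = 0.0001, r1 = 0.53 and r2 − r3 = 0.02. The bracket is 0.47 + 17 × 0.02 = 0.81. The SAP cites a binormal σ_c² without printing it; I assume 0.0099·exp(−a²/2)·[(5a² + 8) + (a² + 8)/4]/n_cancer, with a = 1.414·z(AUC), averaged over AUC 0.80 and 0.75.

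- *60 cancers, 240 non-cancers:* σ_c² = 0.00148; SD = √[(2/18)(0.000532 + 0.00148 × 0.81)] = 0.0139; power for margin 0.05 (t, 17 df) is 92%, matching SAP Table 4.
- *30 and 120:* σ_c² = 0.00296; SD = 0.0180; power 74%, or 76% with σ_c² at AUC 0.80 only.

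The 30/120 split applies the 50% dense target in Protocol 7.3.4 equally to cancers and non-cancers, which the documents do not state. With 40% to 60% dense, power is 66% to 80%. The study was sized for the primary endpoint only, so this illustrates precision and shows no defect.

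**The case for a change.** The best case for a change is that the status has to be inferred. SAP 1.1.2 promises type 1 error protection right after a list that includes endpoint 9. SAP section 4 sets two-sided 0.05 as the default for inference, and nothing exempts endpoint 9. Margins and superiority wording suggest a test. The statistician is not blinded to reading condition, and no time is fixed for deciding whether to analyse or which metric to report.

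Part of this stands. The labelling is inconsistent, the metric is open, and a favourable descriptive result could be picked out for emphasis. But that freedom is bounded: SAP 4.5 names the candidate metrics, and a dense-breast analysis brings the non-dense one with it.

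The rest does not stand. An analysis done similarly can mean the same MRMC method; the sentence that establishes superiority concerns full-set AUC. A margin can serve as a reference line for reading a CI. Saying how an analysis will be done and then making it conditional is not a contradiction. Nor is it right that a dense-breast test would need no earlier rejection, since H1 must be rejected first.

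**Conclusion.** No change is needed. Under SAP 4.6.3 and section 5, endpoint 9 is an optional subgroup analysis reported as estimates with 95% CIs. It holds no alpha, takes none from H1 to H8, and supports no formal non-inferiority or superiority claim. Family-wise error over H1 to H8 remains 0.05. The same scope sentence covers endpoints 6 to 8, which also have no hypothesis in the graph.

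A sentence calling these endpoints descriptive would record a status that an analyst can already read from the SAP; it would alter no test, sample size or primary conclusion. The 2.5% to roughly 12% error figures apply only if a dense-breast result were presented as established contrary to 4.6.3. The 74% to 76% power figure assumes that FFDM AUC 0.80 and the full-sample variance inputs hold in dense breasts. The conclusion rests on the scope sentence being followed when results are reported.
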